## **4. STUDY POPULATION**

Approximately 36 subjects, male and female, 18 years of age or older who meet all the inclusion criteria and none of the exclusion criteria will be enrolled at two United States investigational centers. Subjects will be randomized in a 2:1 ratio with 24 subjects randomized to treatment with ACU-D1 Ointment [REDACTED] and 12 subjects randomized to treatment with ACU-D1 Ointment Vehicle.

## **5. STUDY OBJECTIVE**

The main objective of this study is to evaluate the safety, tolerability and efficacy of ACU-D1 Ointment [REDACTED] when applied twice daily for 12 weeks to papulopustular (Type-2) rosacea (acne rosacea) of the face.

## **6. TRIAL DESIGN**

This is a randomized, double-blind, vehicle-controlled, parallel-group study of ACU-D1 Ointment [REDACTED] and the ACU-D1 Ointment Vehicle in subjects with papulopustular rosacea on the face.

Subjects will be randomized in a 2:1 ratio with 24 subjects randomized to treatment with ACU-D1 Ointment [REDACTED] and 12 subjects randomized to treatment with ACU-D1 Ointment Vehicle

The study will be conducted at two United States investigational centers.

Study visits are:

- Visit 1 (Day -13 to 0) enrollment and start of the screening period
- Visit 2 (Day 1) randomization and start of the study medication treatment period

Accutis, Inc.

Protocol number: ACU-D1-201

- Visit 3 (Day 15) treatment period follow-up
- Visit 4 (Day 29) treatment period follow-up
- Visit 5 (Day 57) treatment period follow-up
- Visit 6 (Day 85) end of the treatment period and start of the no treatment follow-up period
- Visit 7 (Day 99) no treatment follow-up, end of study.

## **6.1. Endpoints**

### **6.1.1. Efficacy Endpoints**

The primary efficacy evaluation is the total lesion count defined as the sum of the papule count, the pustule count, and the nodule count.

The secondary efficacy evaluations are:

- Investigator's Global Assessment score: an ordered categorical value ranging from 0 (Clear) to 4 (Severe)
- Treatment responders: subjects who have either (1) two ordinal or more reductions in the Investigator's Global Assessment (IGA) or (2) an IGA score of 0 or 1

There is one ancillary efficacy evaluation of individual lesion counts: papules, pustule, and nodule counts.

### **6.1.2. Safety Endpoints**

Safety endpoints include:

- Adverse events
- Local tolerability of signs and symptoms of irritation
- Clinical laboratory safety tests
- Vital sign readings
- Urine pregnancy tests

### **6.1.3. Other Endpoints**

Standardized color photographs of the subject's face to document the status of the rosacea being treated will be taken throughout the study. No formal review of these is planned as part of this SAP.

included in this study:

1. Subject is pregnant, nursing or planning to become pregnant during the duration of the study
2. Subject has used systemic glucocorticosteroids within 42 days prior to Visit 1 (inhaled and ocular glucocorticosteroids are permitted)
3. Subject has used systemic antibiotics within 28 days prior to Visit 1
4. Subject has used any topical glucocorticosteroids on the face within 28 days prior to Visit 1
5. Subject has used any prescription or over-the-counter (OTC) product for the treatment of acne or rosacea within 14 days prior to Visit 1
6. Subject is currently using any therapy that, in the investigator's opinion, is a photosensitizer (e.g., phenothiazines, amiodarone, quinine, thiazides, sulphonamides, quinolones, etc.)
7. Subject currently has any skin disease (e.g., psoriasis, atopic dermatitis, eczema), or condition (e.g., actinic keratosis, photo-damage, sunburn, excessive hair, open wounds) that, in the investigator's opinion, might impair evaluation of rosacea or which exposes the subject to an unacceptable risk by study participation
8. Subject currently has, on the face, or has had on the face, any of the following within the specified period prior to Visit 1 that, in the investigator's opinion, might impair evaluation of rosacea or which exposes the subject to an unacceptable risk by study participation:
  - A cutaneous malignancy; 180 days
  - Experienced a sunburn; 14 days
9. Subject has facial hair, that in the investigator's opinion, might impair evaluation of rosacea or proper study medication application
10. Subject has a history of sensitivity to any of the ingredients in the study medications
10. Subject has participated in an investigational drug trial in which administration of an investigational study medication occurred within 30 days prior to Visit 1.

### **7.3. Subject Discontinuation**

Subjects will be informed that they are free to withdraw from the study at any time and for any reason. The investigator may remove a subject from the study if, in the investigator's opinion, it is not in the best interest of the subject to continue the study.

In case of premature discontinuation of study participation, efforts will be made to perform all the Visit 6 assessments for discontinuations during the treatment period and all the Visit 7 assessments for discontinuations during the no-treatment period.

## **8. STATISTICAL CONSIDERATIONS**

The statistical plan describes the statistical analysis as it is foreseen at the time of planning the trial. Any deviation from the statistical plan, the reasons for such deviations, and any additional statistical analyses that may be performed will be submitted as amendments prior to the unblinding of the randomization code.

Categorical variables will be summarized by the count (N) and percentage of subjects (%). Continuous variables will be summarized by the number of non-missing observations (N), mean, standard deviation (SD), median, minimum, and maximum values.

All study data will be displayed in the data listings.

### **8.1. Missing Values and Imputation**

For both MITT and PP analyses, the last non-missing observation (post randomization) of these subjects will be carried forward to any subsequent missing visits and to endpoints.

For analysis purposes, the endpoint analysis will use the last non-missing post-baseline data for each efficacy variable.

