4.6. Subject Discontinuation from the Study

Subjects will be informed that they are free to withdraw from the study at any time and for any reason.

The investigator may remove a subject from the study if, in the investigator's opinion, it is not in the best interest of the subject to continue the study. Subjects may be discontinued due to occurrence of AEs, occurrence of pregnancy or use of a prohibited concomitant therapy. The investigator will notify the Accutis, Inc. study monitor within 24 hours of any subject discontinuation.

In case of premature discontinuation of study participation, efforts will be made to perform all the Visit 6 assessments for discontinuations during the treatment period and all the Visit 7 assessments for discontinuations during the no-treatment period. The date the subject is withdrawn from the study and the reason for discontinuation will be recorded on the subject's case report forms (CRFs). All withdrawn subjects with ongoing AEs will be followed as appropriate.

The study may be discontinued at the discretion of the investigator or Accutis, Inc. Some examples of reasons for discontinuation are the occurrence of the following:

- Increased frequency, severity or duration of known AEs
- Medical, regulatory or ethical reasons affecting the continued performance of the study
- Difficulties in the recruitment of subjects
- Cancellation of the drug development program.

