6.1. Efficacy Evaluations

6.1.1. Lesion count

The Lesion Count is the total number of rosacea acne lesions (*i.e.*, papules, pustules and nodules) on the subject's face.

At Visits 1-7, the investigator will report the total number for each of the following lesion types on the face:

- Papules, defined as raised inflammatory lesions, <0.5cm in diameter with no visible purulent material
- Pustules, defined as raised inflammatory lesions, <0.5cm in diameter with visible purulent material
- Nodules, defined as any circumscribed, inflammatory mass ≥ 0.5 cm in diameter.

The investigator should count each lesion type separately papules first, then pustules then nodules. She/he should start counting at the middle of a subject's forehead moving clockwise ending where she/he started, then count the number of lesions on the nose and report the total number of lesions.

At Visit 1, to be enrolled and at Visit 2 to be randomized the subject must have a total of ≥ 10 and ≤ 40 inflammatory lesions (papules, pustules and nodules) with ≤ 2 nodules, on the face.

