9.2.1. Modified intention-to-treat analysis (MITT)

The modified intention-to-treat (MITT) population will include all randomized subjects who were dispensed study medication and provided any post-baseline efficacy data. The general analysis procedure for any post-baseline visit with missing efficacy data will be to impute data values from the most recent non-missing post-baseline visit. For analysis purposes, the endpoint analysis will use the last non-missing post-baseline data for each efficacy variable.

The safety population will include all randomized subjects. The analysis of safety will include variables such as clinical laboratory evaluations, vital signs, and adverse drug experiences. It is not necessary that measurements of any efficacy variable post randomization be available.

The MITT analysis provides estimates of treatment effects that may be more likely to mirror those effects observed in subsequent practice. Consequently, this analysis will be considered the primary efficacy analysis.

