9.3.2. Statistical analysis of total lesion count

Total lesion count will be summarized for each treatment group and at each visit using mean, standard deviation, median, minimum, and maximum. The comparison between the two treatments will be based on the difference for each subject between each visit and Visit 2.

In accordance with ICH E9 guideline on Statistical Consideration in the Design of Clinical Trials (1998), the type 1 error rate of the test will be 5%.

At each post-baseline visit, an analysis of covariance (ANCOVA) will be performed to test the null hypothesis of no treatment effect. The dependent variable will be the difference between the value at each post-baseline visit, including endpoint, and the baseline value. The change from baseline to the endpoint (Visit 6) will be the primary efficacy analysis. The baseline value will be the covariate. Treatment group and study center will be the main effects in the model. This analysis will be performed on the MITT and PP populations. Efficacy will be declared if the treatment effect p-value for the MITT population is no greater than 0.05 and is favorable to ACU-D1 Ointment [REDACTED].

A second ANCOVA, which includes a treatment-by-center interaction, will be performed in order to test the significance of the interaction term in an exploratory manner. If the interaction term is significant at the 0.10 level, summary data will be presented for each study center in an appendix to the study report. In addition, if the interaction term is significant at the 0.10 level, the interaction term may be included in the final ANCOVA model to examine treatment effects if inclusion of this term increases the sensitivity of the analysis.

The residuals from the primary ANCOVA model will be analyzed for deviations from normality. If the test for normality fails at the 0.05 level of significance then the ANCOVA analysis will be supplemented by a Van Elteren test, stratified by study center.

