### **8.11. Efficacy Analyses**

#### **8.11.1. Primary Efficacy Variables: Lesion Count**

Total lesion count will be summarized for each treatment group and at each visit using mean, standard deviation, median, minimum, and maximum. The comparison between the two treatments will be based on the difference for each subject between each visit and Visit 2.

In accordance with ICH E9 guideline on Statistical Consideration in the Design of Clinical Trials (1998), the type 1 error rate of the test will be 5%.

Proc Mixed in SAS will be used to develop a repeated measures analysis of covariance (ANCOVA) model to test the null hypothesis of no treatment effect. The dependent variable will be the difference between the value at each post-baseline visit, including endpoint, and the baseline value. The change from baseline to the endpoint (Visit 6) will be the primary efficacy endpoint. The baseline value will be the covariate. Treatment group and study center will be the main effects in the model. The mixed model will employ LOCF procedures for missing values. Efficacy will be declared if the treatment effect p-value for the MITT population is no greater than 0.05 and is favorable to ACU-DI Ointment [REDACTED]

A second ANCOVA, which includes a treatment-by-center interaction, will be performed in order to test the significance of the interaction term in an exploratory manner. If the interaction term is significant at the 0.10 level, summary data will be presented for each study center in an appendix to the study report. In addition, if the interaction term is significant at the 0.10 level, the interaction term may be included in the final ANCOVA model to examine treatment effects if inclusion of this term increases the sensitivity of the analysis.

The residuals from the primary ANCOVA model will be analyzed for deviations from normality. If the test for normality fails at the 0.05 level of significance then the ANCOVA analysis will be supplemented by a Van Elteren test using Proc Npar1way in SAS, stratified by study center. Subgroup analyses including but not limited to race, age and gender will be performed for exploratory purposes, provided adequate sample sizes are available in potential subgroups. Subgroups will be analyzed by adding the subgroup as a main effect and the interaction term of subgroup\*treatment to the model.

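### Carry-forward does not stop at the end of treatment, so missing Visit 7 (off-drug) efficacy values are filled with treatment-period values and the Visit 7 comparison can be biased in either direction

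*SAP*

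**What the plan says.** **Imputation rule.** For both the MITT and PP analyses, SAP 8.1 says that "the last non-missing observation (post randomization) of these subjects will be carried forward to any subsequent missing visits and to endpoints". Protocol 9.2.1 covers any post-baseline visit with missing efficacy data, and its general procedure is "to impute data values from the most recent non-missing post-baseline visit". Protocol 9.2.2 carries values forward for the PP set. SAP 8.11.1 adds: "The mixed model will employ LOCF procedures for missing values". None of these sections makes an exception for a visit after treatment has ended.

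**Visits.** SAP 6 describes the last two visits as "Visit 6 (Day 85) end of the treatment period and start of the no treatment follow-up period" and "Visit 7 (Day 99) no treatment follow-up, end of study".

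**Efficacy data at Visit 7.** Protocol 6.1.1 says: "At Visits 1-7, the investigator will report the total number for each of the following lesion types on the face". Protocol 6.1.2 schedules the IGA at the same visits.

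**Comparisons at Visit 7.** Protocol 9.3.2 says: "At each post-baseline visit, an analysis of covariance (ANCOVA) will be performed to test the null hypothesis of no treatment effect". SAP 8.11.1 also models change from baseline at every post-baseline visit. IGA and responder status are compared at each visit (Protocol 9.4.1 and 9.4.2; SAP 8.11.2 and 8.11.3), and individual lesion counts at each post-randomization visit (Protocol 9.4.3; SAP 8.11.4). Visit 7 is therefore a planned comparison for each of them.

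**Dropouts.** Under Protocol 4.6, "efforts will be made to perform all the Visit 6 assessments for discontinuations during the treatment period". Those who leave in the no-treatment period are asked for the Visit 7 assessments instead. SAP 7.3 says the same. Randomized subjects who do not complete are not replaced (Protocol 4.8).

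**The concern.** Visit 7 is the only scheduled occasion on which lesion count and IGA are seen after treatment has stopped. A treatment-period dropout in the MITT or PP set will normally have no Visit 7 value, because the plan does not ask for one. The rule then supplies a value from the treatment period. MITT membership needs only one post-baseline efficacy value (Protocol 9.2.1; SAP 8.2.1), so a Day 15 count could stand as a Day 99 off-drug result.

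The trustworthiness of the Visit 7 tables and tests is at stake. A filled value carries no information about what happens off drug, yet it enters the arm mean as if it did and counts as an observation in the standard error. A reader of the Visit 7 result could not tell how much of any apparent persistence was observed and how much was supplied by the rule.

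**Working it through.** **No plan figure to reproduce.** Protocol 9.7 gives no power calculation. The documents state no effect size, standard deviation or expected dropout. The 24 and 12 subjects agree with 36 at 2:1 (36 × 2/3 = 24; 36 × 1/3 = 12).

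**Step 1: what holds without assumptions about the effect.** Let m be the share of an arm whose Visit 7 value is filled, and D the mean Visit 6-to-7 change among subjects actually seen at Visit 7. A filled subject has the same value at Visits 6 and 7, so the change is 0. The arm's mean change is

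(1 − m) × D + m × 0 = (1 − m) × D.

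This holds whether or not the filled subjects had improved.

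**Step 2: bias in the between-arm comparison.** Measured as spurious benefit to active at Visit 7,

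bias = m_active × (benefit filled active subjects would have lost) − m_vehicle × (the same for vehicle).

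Assumed inputs, none from the documents: on-treatment benefit of 4, 6 or 8 lesions, fully lost off drug; vehicle unchanged; SD 8 lesions; equal missing shares in the two arms. The true off-drug difference is then 0, and the bias is m × benefit. The false-positive rate is a two-sided normal approximation at 0.05 (the documents give 5% without saying one- or two-sided), with SE = 8 × √(1/12 + 1/24) = 2.83.

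| Filled (active, vehicle) | m | Bias, benefit 4 | Bias, benefit 6 | Bias, benefit 8 | False-positive rate at Visit 7 |
|---|---|---|---|---|---|
| 0, 0 | 0 | 0 | 0 | 0 | 5.0% |
| 2/24, 1/12 | 1/12 | 0.33 | 0.50 | 0.67 | 5.2–5.6% |
| 4/24, 2/12 | 1/6 | 0.67 | 1.00 | 1.33 | 5.6–7.6% |
| 6/24, 3/12 | 1/4 | 1.00 | 1.50 | 2.00 | 6.4–10.9% |

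If only half the benefit is lost, each bias halves. For a benefit of 6 and m = 1/6 it is 1/6 × 3 = 0.5 lesion.

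**Step 3: simulation check.** There were 20,000 simulated trials per scenario with 24 and 12 subjects, a 6-lesion benefit fully lost off drug, and 4/24 and 2/12 missing. Differences are active minus vehicle, so negative values favour active.

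| Who is missing | With carry-forward | Observed values only |
|---|---|---|
| At random | −1.02 | −0.02 |
| From the worse half of each arm | −1.02 | −0.06 |
| From the better half of each arm | −1.00 | +0.03 |

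The true difference is 0. Two features of this set-up matter. Every active subject was given the same benefit, so even the worse half carries it forward. The selection was also the same in both arms, which is why the observed-only result stays near 0.

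**Step 4: the opposite direction.** Suppose 4 of 24 active subjects leave with no improvement (change 0), no vehicle subject is missing, and everyone would have a change of −4 at Visit 7. Carry-forward gives an active mean of (20 × −4 + 4 × 0)/24 = −3.33. The difference is −3.33 − (−4) = +0.67 lesion, against active.

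**The case against.** **Direction.** A reader might infer that the rule will make the drug look durable. The documents do not support that. It requires missing Visit 7 data, benefit in the particular subjects who are missing, and loss of that benefit off drug, and the documents give no figure for any of these. Step 4 shows the bias going the other way, and worsening among filled vehicle subjects would offset it. This objection stands, so the direction is conditional.

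**Who is filled.** A reader might infer that every treatment-period dropout appears at Visit 7 with a strictly on-drug value. That is also too strong. Dropouts with no post-baseline efficacy value are outside the MITT set. An early-termination assessment may come some days after the last application; Protocol 5.6.8, for example, removes subjects unable to apply twice daily for more than 4 consecutive days. Subjects who leave after Visit 6 are asked for Visit 7 assessments. The affected group is mainly treatment-period dropouts, with values from the treatment period or shortly after it.

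**Consequence.** A reader might infer that the efficacy decision is compromised. Protocol 9.3.2 and SAP 8.11.1 tie the primary analysis to change at Visit 6, and no objective or endpoint concerns durability. The SAP does not say whether Visit 7 rows enter its repeated-measures model. That is an open question, not evidence that the primary result is affected. Visit 7 also serves safety purposes (adverse events, vital signs, pregnancy test, local tolerability), which this point leaves untouched.

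**Visibility and remedy.** SAP 8.7 tabulates attendance by visit and SAP 8 lists all data, so missing Visit 7 values could be traced. Tracing them does not correct the Visit 7 estimates. An observed-only analysis describes the subjects who returned and has its own selection bias if the reasons for leaving differ by arm. That is true, and it is why n and a note belong with the result.

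After these points, the core remains: the rule as written places treatment-period values in the only off-drug visit, where they show zero change by construction.

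**Conclusion.** The point holds for the Visit 7 efficacy results. With share m filled, an arm's Visit 6-to-7 change is shrunk to (1 − m) of that in the subjects seen, whatever the direction of effect. The between-arm bias depends on who is missing. Under the assumed 6-lesion benefit fully lost off drug, with vehicle unchanged and 1/6 missing per arm, it is about 1.0 lesion toward active. Carried non-response can reverse the sign, and with complete Visit 7 data there is no effect. Benefit, SD and missing shares are all assumptions. This is a cheap improvement on a non-primary visit and does not show a defect in the Visit 6 primary endpoint.

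**What to change.** In SAP 8.1 and Protocol 9.2.1 and 9.2.2, state that carry-forward applies to Visits 3–6 only. Summarize and compare Visit 7 lesion counts, IGA and responder status on observed values, show the number observed per arm, and note that these results describe subjects who returned. In SAP 8.11.1, add that the carry-forward used in the mixed model has the same limit.

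The cost is a short text change in both documents. The protocol change needs IRB approval (Protocol 11.1), and both documents provide for analysis changes by amendment before unblinding (Protocol 9.1; SAP 8). The Visit 7 set becomes smaller and consists of completers. With 1/6 missing it would be 20 and 10 subjects instead of 24 and 12. At the assumed SD of 8, the standard error rises from 2.83 to 8 × √(1/20 + 1/10) = 3.10, which reflects the information actually collected. The Visit 6 endpoint analysis keeps its planned carry-forward.

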9.2.2. Per-protocol analysis (PP)

The per-protocol (PP) population is a subset of the MITT population and includes subjects who have no violations of the inclusion/exclusion criterion and who are compliant with treatment medication, defined as greater than or equal to 80% of specified medication. Before breaking the blind the precise reasons for excluding subjects from the PP population will be fully documented in a blinded data review meeting.

The last non-missing observation (post randomization) of these subjects will be carried forward to any subsequent missing visits and to endpoint.

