9.4. Secondary Efficacy Variables and Their Statistical Analyses

9.4.1. Investigator's global assessment

The Investigator's Global Assessment score is an ordered categorical value ranging from 0 (Clear) to 4 (Severe). The assessment is obtained at each visit.

Investigator's Global Assessment score will be summarized for each treatment group and at each visit using the median, minimum, maximum and frequency distributions. The comparison between the two treatments will be based on the difference for each subject between each visit, including the endpoint visit, and the baseline visit.

The van Elteren test, stratified by study center, as defined for the primary efficacy variable will be used for the analysis of IGA. Ordinal logistic regression models of the IGA, parameterized in the same manner as the ANCOVA models for the primary efficacy variable, will be used in an exploratory analysis of the impact of treatment on IGA scores.

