**8.11.2. Secondary Efficacy Variable: Investigator's global assessment**

The Investigator's Global Assessment score is an ordered categorical value ranging from 0 (Clear) to 4 (Severe). The assessment is obtained at each visit. Investigator's Global Assessment score will be summarized for each treatment group and at each visit using the median, minimum, maximum and frequency distributions. Percent Change from baseline will be summarized for each follow-up visit. The comparison between the two treatments will be based on the difference for each subject between each visit including the endpoint visit, and the baseline visit. The van Elteren test, stratified by study center, as defined for the primary efficacy variable will be used for the analysis of IGA. Ordinal logistic regression models of the IGA, parameterized in the same manner as the ANCOVA models for the primary efficacy variable, will be used in an exploratory analysis of the impact of treatment on IGA scores.

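### The endpoint rule is not capped at Visit 6, so read literally it picks off-treatment Visit 7 values and conflicts with the stated primary endpoint

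*SAP*

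**What the plan says.** **General rule.** SAP 8.1 states that "the endpoint analysis will use the last non-missing post-baseline data for each efficacy variable". Protocol 9.2.1 has the same rule. Neither limits it to the treatment period.

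**Carry-forward.** The preceding sentence of SAP 8.1 says that for both the MITT and PP analyses "the last non-missing observation (post randomization) of these subjects will be carried forward to any subsequent missing visits and to endpoints". Protocol 9.2.2 says of the PP subjects that their last post-randomization value "will be carried forward to any subsequent missing visits and to endpoint".

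**Primary variable.** Here a visit is named. Protocol 9.3.2: "The change from baseline to the endpoint (Visit 6) will be the primary efficacy analysis". SAP 8.11.1: "The change from baseline to the endpoint (Visit 6) will be the primary efficacy endpoint". The SAP model is specified as follows: "The dependent variable will be the difference between the value at each post-baseline visit, including endpoint, and the baseline value".

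**IGA and responders.** No visit is named. The IGA comparison is of differences "between each visit, including the endpoint visit, and the baseline visit" (Protocol 9.4.1) and "between each visit including the endpoint visit, and the baseline visit" (SAP 8.11.2). Protocol 9.4.2 and SAP 8.11.3 define responders by visit and at endpoint, and treat the endpoint result as the main responder analysis, again without a visit number.

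**Schedule.** Treatment stops at Visit 6 (Day 85), and Visit 7 (Day 99) is an untreated follow-up visit (Protocol 5.1, SAP 6). Lesion count and IGA are recorded at all seven visits (Protocol 6.1.1, 6.1.2 and 5.4.7). A subject who leaves during the no-treatment period should, where possible, have the Visit 7 assessments (Protocol 4.6, SAP 7.3).

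**The concern.** Visit 7 is post-baseline and carries efficacy data. For any subject who attends it, the last non-missing post-baseline value is therefore the Visit 7 value. One rule in the plan gives an end-of-treatment endpoint. The other, applied as written, gives an off-treatment endpoint to everyone with Visit 7 data.

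The study objective concerns 12 weeks of twice-daily application (Protocol 3, SAP 5), and a Day 99 value taken after treatment has stopped does not measure that. The exposure is greatest for IGA and responders, because the only written definition covering every efficacy variable is the uncapped one. If the choice of visit were left open until after unblinding, it could be made with the results in view.

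**Working it through.** The plan has no figure of its own to reproduce on this point. The check applies the rules to the visit schedule.

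**Inputs** (Protocol 5.4.3 to 5.4.7), in days after Visit 2:

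| Visit | Nominal | Window | Status |
|---|---|---|---|
| 3 | 14 | 10–18 | on treatment |
| 4 | 28 | 24–32 | on treatment |
| 5 | 56 | 52–60 | on treatment |
| 6 | 84 | 80–88 | end of treatment |
| 7 | 98 | 94–102 | off treatment |

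Four of the five post-baseline efficacy visits fall in or at the end of treatment, and one falls after it.

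**Step 1. Which visit supplies the endpoint.** The literal rule takes the latest non-missing value from Visits 3–7. The capped rule takes the latest from Visits 3–6.

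| Attendance | Literal | Capped |
|---|---|---|
| All visits | 7 | 6 |
| Misses Visit 7 | 6 | 6 |
| Misses Visit 6, attends Visit 7 | 7 | 5 |
| Stops after Visit 4, Visit 6 assessments done on leaving | 6 | 6 |
| Stops after Visit 4, nothing further | 4 | 4 |
| Visit 7 is the only post-baseline visit | 7 | none |

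The rules differ only for subjects with Visit 7 data. Subjects who stop during treatment and have no later visit contribute the same value under either.

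**Step 2. How far the endpoint moves when Visits 6 and 7 are both attended.** Nominal: 98 − 84 = 14 days. Shortest: 94 − 88 = 6. Longest: 102 − 80 = 22.

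**Step 3. Visit 6 missed, Visit 7 attended.** The two sentences of SAP 8.1 now disagree with each other. Carrying forward to a Visit 6 endpoint uses the last earlier value; the last-non-missing sentence uses Visit 7. The gap depends on the last earlier visit attended:

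- Visit 5: 98 − 56 = 42 days (94 − 60 = 34 to 102 − 52 = 50).
- Visit 4: 98 − 28 = 70 days (94 − 32 = 62 to 102 − 24 = 78).
- Visit 3: 98 − 14 = 84 days (94 − 18 = 76 to 102 − 10 = 92).

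The last two need Visit 5, or Visits 4 and 5, to be missed as well, so they should be rare.

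**Step 4. How many subjects.** With the cap, 0 of 36 have an off-treatment endpoint. Under the literal rule, every Visit 7 attender does. The documents give no attendance rate; assuming 75% to 100%, that is 0.75 × 36 = 27 to 1.00 × 36 = 36.

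**Step 5. The primary model.** SAP 8.11.1 lists endpoint in addition to the post-baseline visits and does not exclude Visit 7. Read literally, Visit 7 enters the repeated-measures model behind the efficacy declaration, and the endpoint value might be entered a second time as its own record. Protocol 9.3.2 fits a separate ANCOVA at each visit, so a duplicated record would not arise there.

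**The case against.** The strongest reply is that Visit 6 is plainly intended. Both primary-analysis sections name it, and a specific section normally governs a general one. The uncapped sentence sits with the missing-data rules in both documents, so it can be read as saying only how a missing endpoint is filled. Visit 6 is the only visit ever called endpoint, and a single endpoint visit fits poorly with a last value that varies by subject. The table shells, which SAP 9 places in a separate document not available here, may name the visit.

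Most of this stands as evidence of intent, and for the primary variable a careful reader would probably settle on Visit 6. It does not remove the conflict. The sentence is not conditioned on missing data and covers every efficacy variable. If endpoint simply meant Visit 6 after carry-forward, the sentence would be redundant. The plan also repeatedly lists endpoint separately from the scheduled visits, which invites a programmer to derive a separate last-observation record. For IGA and responders, Visit 6 has to be inferred by analogy. Table shells could show the intent, but the rule in the plan would still contradict them.

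Two further objections are fair. The subject count rests on assumed attendance and shows nothing about the results. And which contrast from the repeated-measures model is primary is partly a separate model-specification question; what belongs here is only whether Visit 7 and an extra endpoint record enter that model.

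**Conclusion.** The concern holds. The endpoint rule in SAP 8.1 and Protocol 9.2.1 has no limit at Visit 6, contradicts the primary endpoint as stated in both documents, and is not overridden by a visit number for IGA or responders. Followed exactly, it replaces an end-of-treatment value with one taken a nominal 14 days later (6 to 22), off treatment, for every subject with Visit 7 data: 27 to 36 of 36 under the assumed 75% to 100% attendance, against none with a cap.

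The size and direction of any effect on the treatment comparison cannot be derived. That would require knowing how lesion counts and IGA change after treatment stops, and the documents do not say. No effect on p-values or power is claimed. The point should be corrected before unblinding, because the plan states a rule that gives the wrong endpoint when applied as written.

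**What to change.** 1. In SAP 8.1 and Protocol 9.2.1, with a cross-reference from Protocol 9.2.2, replace the endpoint sentence for lesion counts, IGA and responders with: *Endpoint is the Visit 6 assessment or, if that is missing, the last non-missing post-baseline value obtained before it. Visit 7 is summarised separately as off-treatment follow-up and is never used as endpoint.* Make clear that Visit 6 assessments done early, on leaving during treatment, count as Visit 6.
2. Name Visit 6 as the endpoint in SAP 8.11.2 and 8.11.3 and in Protocol 9.4.1 and 9.4.2.
3. In SAP 8.11.1, state that the primary test is the treatment difference at Visit 6, that Visit 7 data do not contribute to it, and that endpoint is not entered as an additional record.
4. State how the endpoint analysis handles a subject whose only post-baseline efficacy data are from Visit 7. Such a subject qualifies for MITT (SAP 8.2.1) but has no capped endpoint.
5. Check that the table shells use the same definition.

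The cost is a few sentences and one visit condition in the derivation program, with no change to visits or data collection. The protocol edits need IRB approval as an amendment (Protocol 11.1). The changes should be made before the code is broken, as Protocol 9.1 and SAP 8 require of changes to the statistical plan.
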